part of the procedure as well as the total procedure time, and reduce the number of recurrences by long term follow-up.

Purpose:

The purpose of this study is to investigate surgical work space and surgical conditions in patients scheduled for laparoscopic umbilical, -linea alba and incisional herniotomy. The patients will act as their own control with evaluation of surgical work space and surgical conditions during both deep NMB and no NMB.

Hypothesis:

Deep NMB defined as TOF=0 and post-tetanic count (PTC) ≥ 1 , will give better surgical workspace, better surgical conditions, as well as shorter duration of surgery and reduced number of recurrences of hernias compared with no NMB.

Method:

See appendix 1, flow diagram.

Design:

Randomized, cross-over design, with blinding of patient and surgeon. Randomization is used to determine the treatment sequence (no NMB followed by deep NMB (Group A) or deep NMB followed by no NMB (Group B)) in order to blind the surgeon.

Outcomes:

Primary outcome:

Improvement of surgical workspace (rated on a 5-point scale) estimated as the difference between the workspace during deep NMB and the workspace without NMB. Ratings are performed in the same patient during stable pneumoperitoneum at 12 mmHg.

Protocol
The hernia study
September 16. 2016

Secondary outcomes: (comparing Group A with Group B)

- Surgeon's rating of surgical conditions while suturing the hernia (5-point rating scale)
- Duration of operating time (from first incision to last suture)
- Assessments if the surgical space is better, unchanged or worse when evaluating before and after the intervention
- Number of sudden contractions of the abdominal wall during operation (bucking or coughing),
- Number of insufflator alarms where pneumoperitoneum > 17 mmHg,
- Number of episodes with continuous abdominal contractions where the abdomen feels "tight" but the operation can still proceed (the intestines are gradually displaced near the inner surface of the abdominal wall).
- Number of recurrences of hernias by 2 year follow-up (separate publication). Patients will 2 years after operation receive a letter with invitation to ambulatory clinical assessment by a surgeon at Herlev Hospital or have the opportunity to receive a visit by a surgeon at their home address.

Number of patients:

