34 eligible patients allocated into an assessor-blinded randomized cross-over design: one group first receives deep NMB followed by no NMB and the other group first receives no NMB followed by deep NMB.

Protocol
The hernia study
September 16. 2016

Groups:

Group A: After intubation and placement of trocars: Bolus of saline (placebo) 6 ml. After three minutes the surgeon assesses the surgical workspace with pneumoperitoneum 12 mmHg. Bolus of rocuronium 0,6 mg/kg When TOF=0 the surgical workspace is assessed again.

Group B: After intubation and placement of trocars: Bolus of rocuronium 0.6 mg/kg When TOF=0 the surgeon assesses the surgical workspace with pneumoperitoneum 12 mmHg. Sugammadex is administered and when TOF=100% the surgical workspace is assessed again[8].

Criteria for participation:

Inclusion criteria:

Patients \geq 18 years old

Elective laparoscopic umbilical herniotomy, incisional herniotomy and linea alba herniotomy.

Can read and understand Danish

Informed consent

Exclusion criteria:

Known allergy to sugammadex, rocuronium or mivacurium

Known homozygous variants in the butyrylcholinesterase gene

Protocol
The hernia study
September 16. 2016

Severe renal disease, defined by S-creatinine > 0.200 mmol/L, GFR < 30ml/min or hemodialysis)

Neuromuscular disease that may interfere with neuromuscular data

Lactating or pregnant (Women of child bearing potential must take a urine pregnancy test at the day of the operation. The test will be provided by the hospital staff).

Indication for rapid sequence induction

Withdrawal criteria:

- In case of cancelling the operation, the patient will not receive the intervention. Data will not be available and therefore not analyzed and the patient will be considered as a "dropout".
- In case of the patient not receiving the intervention (trial medicine/placebo) after randomization, the data will not be analyzed and the patient will be considered as a "dropout".

These "dropout" patients will be disclaimed further data analysis.

Major violation:

- In case of need for increasing pneumoperitoneum to > 12 mmHg due to poor surgical conditions
- Converting to laparotomy

These will be characterized as major violations. The data will be analyzed in the intention-to-treat analysis, but excluded from the per-protocol analysis.

End of study:

When 34 patients have been evaluated considering the primary endpoint according to the intention-to-treat analysis, the study is finished.

Patient information:

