Postoperative pain treatment with paracetamol, NSAID and morphine according to local guidelines.

PONV profylaxis:

I.v. dexamethason 8 mg routinely

Data collection

Perioperative data collection that will be noted in CRF:

Type of operation with operation code

Batch-number, expiration date, used and surplus quantities of rocuronium and sugammadex, TOF values (NMB sheet)

Body temperature measured immediately after intubation and again immediately before extubation

Size of hernia defect measured during operation just before the defect is sutured

Surgical ratings on 5 point scale

Operating time (from first incision to last suture)

Number of sudden abdominal contractions and episodes with “tight” abdomen

Need for additional NMB to optimize surgical conditions

Postoperative registration:

Number of patients with recurrences of hernias 2 years after herniotomy.

Statistics:

Eligible patients and excluded patients will be registered at a screening list.

Data from all randomized patients, who receive the intervention, will be included in the intention-to-treat analysis.

Patients, included in the intention-to-treat analysis, but who are categorized as major violation, will be excluded from the per-protocol analysis.

Normal distributed variables will be expressed by means and standard deviation; variables that are not normal distributed will be expressed by medians and interquartile range and the Mann-Whitney U test used for comparison of the median values.

Fisher's exact test will be used at comparisons of percentages. A p value < 0.05 is considered significant.

As the study is a crossover trial, it is necessary to test for a possible period effect and a treatment period interaction. To detect a possible period effect a two sample t test to compare the differences between the periods in the two groups of patients will be carried out. If there is no general tendency for patients to do better in one of the periods, we assume that the mean differences between the periods to be of the same size but with opposite signs.

To investigate the possibility of a treatment-period interaction a two sample t test will be carried out by noticing, that in the absence of an interaction, the patients response to the treatment will be the same regardless of the order in which it is received.

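### The per-protocol set drops patients for events that poor surgical conditions can cause, so its estimate is open to selection bias, probably but not necessarily towards no effect

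*Combined protocol and SAP*

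**What the plan says.** The section on major violations lists two triggers: "In case of need for increasing pneumoperitoneum to > 12 mmHg due to poor surgical conditions" and "Converting to laparotomy". For both, "The data will be analyzed in the intention-to-treat analysis, but excluded from the per-protocol analysis". The Statistics section repeats that patients "who are categorized as major violation, will be excluded from the per-protocol analysis". Neither place limits when in the operation the event must occur, and no other reason for per-protocol exclusion is listed.

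The primary outcome is "estimated as the difference between the workspace during deep NMB and the workspace without NMB", and "Ratings are performed in the same patient during stable pneumoperitoneum at 12 mmHg". The secondary outcomes compare Group A with Group B. They include the rating while suturing, operating time, abdominal contractions and insufflator alarms. In that phase Group A is on a rocuronium infusion and Group B has been reversed (Medicine according to intervention).

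The intention-to-treat set is wider: "Data from all randomized patients, who receive the intervention, will be included in the intention-to-treat analysis". It also ends the trial: "When 34 patients have been evaluated considering the primary endpoint according to the intention-to-treat analysis, the study is finished". The plan does not say what role the per-protocol result has or how a disagreement with intention-to-treat would be read.

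**The concern.** A per-protocol set normally removes patients whose treatment or measurement did not follow the plan. Here the first trigger names poor surgical conditions as its cause, and conversion can have the same cause. Workspace and surgical conditions are the primary outcome and the first-listed secondary outcome. Membership of the set is therefore decided after randomisation by something the outcome can bring about.

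Two things follow.

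- A patient rated twice at stable 12 mmHg, whose pressure is raised later during suturing, has complete and valid primary data but is still dropped.
- For the Group A versus Group B outcomes, the groups may lose different numbers and different kinds of patient, so the remaining comparison is no longer a randomised one.

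If the two analyses then disagree, the disagreement may come from the exclusion rule but be read as a lack of robustness. If they agree, that is weaker support than it looks.

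**Working it through.** **1. The plan's own figure.** Inputs from the sample size section: difference 1, SD 2, alpha 0.05 (two-sided assumed), power 0.80. The paired normal formula gives n = (2 × (1.960 + 0.842) / 1)² = 31.4, so 32. The exact paired t calculation gives 34 with power 0.808. The planned 34 is reproduced. With the same inputs, a per-protocol set of 31, 28 or 25 patients has power 0.77, 0.72 or 0.67.

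**2. What an exclusion does to the paired mean.** If m of 34 patients are excluded,

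per-protocol mean = full mean − [m / (34 − m)] × (mean difference in the excluded − full mean).

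The multiplier is 1/33 = 0.03 for m = 1, 3/31 = 0.10 for m = 3 and 6/28 = 0.21 for m = 6. With m = 0 there is no bias. The sign depends on who is excluded:

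- Patients who were poor without neuromuscular blockade (NMB) tend to have a large difference, so dropping them lowers the estimate.
- Patients who were poor under deep NMB tend to have a small or negative difference, so dropping them raises it.

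The exclusion rule names no NMB state, so it admits both.

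**3. Size under a pure rule.** Assumed: unrounded normal ratings, means 3 and 4, SD of the difference 2, correlation 0, true difference 1.00. Results for 10% / 20% excluded:

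- poor without NMB: paired difference 0.73 / 0.51
- poor under deep NMB: 1.28 / 1.50
- poor in the state held while suturing (A deep, B none): paired 0.89 / 0.86 and A−B 0.73 / 0.60, with Group B losing 16% / 29% and Group A 4% / 11%

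The third rule is closest to the trial and moves both contrasts towards no effect.

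**4. Adding the rescue step.** The section on surgical conditions gives a saline bolus in Group A and mivacurium in Group B when conditions are poor after the intervention. It does not say where raising the pressure comes in that sequence. If mivacurium works, some Group B pressure increases may be averted. Let f be the fraction of Group B exclusions that remain.

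Assumed model: rating without NMB is N(3, SD 1.2), rounded and clipped to 1–5. Rating under deep NMB is 4 + 0.5 × (no-NMB rating − 3) + N(0, 1), also rounded and clipped. Exclusion probability is 50%, 25% and 5% for a suturing-state rating of 1, 2 and 3. The full value is 0.89 for both contrasts.

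| f | Paired | A−B |
|---|---|---|
| 1 (rescue changes nothing) | 0.86 | 0.78 |
| 0.5 | 0.88 | 0.87 |
| 0.25 | 0.90 | 0.92 |
| 0 | 0.91 | 0.96 |

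At f = 1, Group B loses 13% and Group A 4%. The sign of the bias changes between f = 0.5 and f = 0.25.

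**5. Other assumptions, same model.** Excluding on the no-NMB rating in both groups removes 13% and brings the paired difference to 0.78. Excluding on it in Group B only removes 6% and gives 0.84 paired and 0.70 for A−B. A heavier rate (80%, 40%, 10%) in Group B only gives A−B 0.56.

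**6. A second model.** Rounded ratings with means 3 and 4, SD of the difference 2, correlation 0, and half of those rated 2 or lower excluded. The full paired value is 0.82. The per-protocol value is 0.76, 0.83, 0.86 and 0.90 for f = 1, 0.5, 0.25 and 0. The reversal does not depend on one choice of model. Conversion was not modelled separately.

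**The case against.** Three points on the other side carry weight.

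- **These are procedural departures.** The sections on pneumoperitoneum and surgical method specify laparoscopic surgery at 12 mmHg, and the primary rating is conditional on that pressure. A reader might infer that neither event belongs among protocol deviations. The documents do not support that: both depart from the specified procedure. What stands is narrower. A departure caused by the outcome is a poor reason for exclusion, particularly when it comes after both primary ratings.
- **The direction is not fixed.** A reader might infer that the per-protocol result must be biased towards no effect. That ignores the unequal rescue and the fact that the rule names no NMB state. It holds only as the more likely direction under the trial's own hypothesis.
- **Little depends on the per-protocol set.** Intention-to-treat keeps these patients, ends the study and supplies the primary test on all 34. No decision in the plan is tied to the per-protocol result. This limits the importance of the point but does not remove it, since the plan announces a per-protocol analysis and leaves its role open.

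It can also be said that these are the only two per-protocol exclusions, so removing them leaves the set undefined. That is correct, and the fix has to supply other criteria.

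**Conclusion.** The point holds as a selection problem in the per-protocol set. The set is chosen after randomisation on events that poor conditions can cause, and it discards patients whose primary data are complete and valid.

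The bias is probably towards no effect if Group B, suturing without a block, has more pressure increases. It can run the other way if mivacurium averts enough of them. The size cannot be stated because the documents give no violation rate. The simulated shifts rest on assumed ratings and exclusion rates, and they show only that the sign and size depend on facts the plan does not supply.

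A reader might go further and infer that the primary result is compromised. It is not: the primary test uses the intention-to-treat patients. The change is worth making, but the trial's main conclusion does not depend on it.

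**What to change.** - **Primary outcome.** Keep in the per-protocol set every patient whose two ratings were taken at stable 12 mmHg. Exclude only if a primary rating was not taken at 12 mmHg, or if the allocated block state was not reached at a rating.
- **Group A versus Group B secondary outcomes.** Do not exclude for a pressure increase or conversion. Use ratings taken before the event where they exist.
- **Reporting.** Give the number of pressure increases and conversions by group, as an outcome.
- **Roles.** State that intention-to-treat is primary and per-protocol supportive.

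The cost is mostly wording. The CRF items under Data collection name neither event, so a line for the event and its time may be needed. Operating times will include some patients operated on at a higher pressure or converted, and some suturing ratings at 12 mmHg may not exist. No change to clinical management is involved.

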At the end of surgery and to reverse first intervention the neuromuscular blockade is reversed with sugammadex/placebo. Sugammadex 2 mg/kg is given if TOF>2, and 4 mg/kg if TOF <2 and 16 mg/kg if PTC < 1. If TOF > 0.90 placebo reversal (NaCl) is given. Neuromuscular monitoring continues until TOF>0.90, stable over 2 min. The patient is awakened and taken to the recovery room.

Capped vials, ampoules, etc. for the test substances, i.e., rocuronium, sugammadex, are discarded after batch number, quantities removed from vials and quantities administered are registered on the NMB sheet.

Pneumoperitoneum:

Pneumoperitoneum is initiated after intubation and the operation will be performed at pneumoperitoneum 12 mmHg.

Surgical conditions:

The surgeon will evaluate the surgical workspace on a 5 point subjective rating scale 3 minutes after first intervention with rocuronium/saline and again three minutes after second intervention with rocuronium/sugammadex. Pneumoperitoneum is maintained at 12 mmHg. Additionally, the surgeon will assess if the surgical space is better, unchanged or worse when evaluating before and after the second intervention. Surgical workspace will also be evaluated while suturing the hernia. Evaluation of surgical work space will consider the assessment of the distance between the intestines and inner surface of the abdominal wall in a standardized manner.

Protocol
The hernia study
September 16. 2016

During operation the surgeon will evaluate the surgical conditions on a 5 point rating scale while suturing the hernia with the use of IPOM technique and finally after the fascial closure. Evaluation will consider tightness or contractions of the abdominal wall muscles affecting the suturing.

Also the number of insufflator alarms for pneumoperitoneum > 17 mmHg will be registered.

In case of need for anesthetic intervention due to poor surgical conditions (with normal BIS, pulse and blood-pressure) after administration of intervention (rocuronium/sugammadex) this will be done in a standardized manner:

Group A: bolus saline (placebo) and wait for three minutes. Then the operation will proceed.

Group B: bolus of mivacurium and wait for three minutes. Then the operation will proceed.

Three minutes after bolus administration the surgeon will evaluate the surgical space and operating conditions on the 5 point rating scales.

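### The sugammadex reversal rule leaves one TOF state without an instruction and gives two instructions in others, and the Group B no-block rating has two triggers that can disagree

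*Combined protocol and SAP*

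**What the plan says.** **Reversal rule (Medicine according to intervention, Both groups).** Its scope is "At the end of surgery and to reverse first intervention the neuromuscular blockade is reversed with sugammadex/placebo". The doses are "Sugammadex 2 mg/kg is given if TOF>2, and 4 mg/kg if TOF <2 and 16 mg/kg if PTC < 1". The next sentence reads "If TOF > 0.90 placebo reversal (NaCl) is given". Then comes "Neuromuscular monitoring continues until TOF>0.90, stable over 2 min", followed directly by "The patient is awakened and taken to the recovery room".

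**Group B sequence (Groups).** First rating, after rocuronium: "When TOF=0 the surgeon assesses the surgical workspace with pneumoperitoneum 12 mmHg". Second rating: "Sugammadex is administered and when TOF=100% the surgical workspace is assessed again". The Group B entry under Medicine according to intervention adds that the sugammadex dose follows the depth of block.

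**Timing (Surgical conditions).** Both workspace ratings are placed three minutes after the respective study drug. No TOF value is attached to that time.

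**Use in the analysis (Primary outcome; Statistics).** The primary outcome is the within-patient difference between the deep-block and no-block ratings. The Wilcoxon signed-rank test on all 34 patients is planned on condition that neither a period effect nor a treatment-period interaction is found.

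**The concern.** Two separate matters are involved.

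The first is a dosing rule that does not give exactly one instruction for every state a patient can be in. Because the rule also covers reversal of the first intervention, it reaches the crossover step in Group B as well as the end of surgery in both groups. A missing or double instruction bears on patient safety and on how uniformly the crossover is carried out.

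The second bears on the primary outcome. In Group B the no-block state exists only because rocuronium has been reversed. If one section waits for TOF=100% and another sets a fixed time, two staff following the same protocol could rate at different degrees of recovery. Group A's no-block rating follows saline before any rocuronium, so it does not share this problem. The distortion would therefore fall on one sequence only, about 17 of the 34 patients at 1:1 allocation (34/2).

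**Working it through.** **1. The plan's own figure.** The sample size of 34 reproduces with an exact paired t calculation (difference 1, SD of differences 2, two-sided 5% assumed): power is 0.795 at n=33 and 0.808 at n=34. Nothing below changes it.

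**2. The reversal rule, state by state.** Inputs are the four conditions in the Both groups paragraph. Two facts link the scales. Under Monitoring, PTC is measured once TOF=0, so PTC below 1 implies a count of 0. A TOF ratio, in its standard definition, needs a fourth response, so a ratio above 0.90 implies a count of 4.

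| State | Instructions met, read literally |
|---|---|
| Count 0, PTC below 1 | 4 mg/kg and 16 mg/kg |
| Count 0, PTC 1 or more | 4 mg/kg |
| Count 1 | 4 mg/kg |
| Count 2 | none |
| Count 3 | 2 mg/kg |
| Count 4, ratio 0.90 or less | 2 mg/kg |
| Count 4, ratio above 0.90 | 2 mg/kg and placebo |

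That is one gap and two overlaps. The placebo overlap arises because TOF is a count in one sentence and a ratio in the next.

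**3. Which defects are reachable at the Group B crossover.** Group B is rated at TOF=0 and then given sugammadex. If reversal follows at once, the count is 0 when the dose is chosen, so the count-2 gap and the ratio overlap are not met there. The PTC overlap can be: Groups sets TOF=0 for that rating without any PTC condition, although the Hypothesis section defines deep block as TOF=0 with PTC of at least 1.

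**4. The two triggers for the Group B no-block rating.**

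- Groups: when TOF=100%, however long that takes.
- Surgical conditions: three minutes after the second study drug, whatever the TOF.

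They agree only if TOF reaches 100% at three minutes. If recovery is slower, the time rule gives a rating before TOF=100%. The documents give no recovery times, so how often this would happen cannot be worked out.

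**5. Direction of the effect.** Let m be the mean no-block rating, d the true gain from deep block, and f the share of that gain still present at the Group B second rating (unknown, between 0 and 1). Assume no true period effect.

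- Group A: m, then m + d. Deep minus none = d.
- Group B: m + d, then m + fd. Deep minus none = d(1 − f).
- Pooled, equal groups: [d + d(1 − f)]/2 = d(1 − f/2).
- Interaction test (patient totals): 2m + d in A and 2m + d + fd in B, a gap of fd.
- Period test (first minus second): −d in A and d(1 − f) in B. These no longer mirror each other; their sum is −fd.

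Any f above 0 dilutes the pooled difference and pushes both preliminary tests away from their null. The Statistics section states no alternative primary analysis if either test is positive.

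**The case against.** **The TOF>0.90 sentence is not a rating rule.** A reader might infer that the 0.90 stop contradicts TOF=100%, so that Group B could be rated as reversed at 0.91 to 0.99. The documents do not support this. The sentence ends monitoring and is followed by awakening the patient, and a patient at 100% also exceeds 0.90. The scope sentence extends the reversal rule to the crossover; it does not make the monitoring stop a trigger for the rating. This objection stands.

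**The gap and the placebo line belong mainly to the end of surgery.** This stands, provided Group B is reversed straight after its TOF=0 rating. They remain gaps in a drug rule for trial patients, but they come after the two primary ratings.

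**The overlaps could be settled by letting the later condition override.** That is a natural reading, but the text does not state it, and no reading order supplies an instruction for a count of 2.

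**Residual abdominal block may be slight.** The Background describes the abdominal muscles and diaphragm as more resistant than the thumb, so incomplete recovery at the thumb may leave little block where the surgeon looks. This is fair. A reader might also want to turn an assumed residual effect into a loss of power. Nothing in the documents supports a value for f, or its application to every Group B patient, and the planned test is a Wilcoxon test rather than a t test. No such loss is claimed.

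**Most of the data are already captured.** TOF is measured every 15 seconds, collected by computer and noted on the NMB sheet. This stands; at most a time mark tying each rating to those values is missing.

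**The flow diagram in Appendix 1 was not available.** It might clarify the sequence, but it would not remove the conflicting text.

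**Conclusion.** The point holds in two parts.

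First, the reversal rule contradicts itself: one state has no instruction, two states meet two, and TOF is unlabelled as count or ratio. At the Group B crossover only the overlap at TOF=0 with PTC below 1 is clearly reachable.

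Second, the Group B no-block rating has two triggers that can disagree. If the time rule is followed before recovery is complete, the primary difference shrinks in Group B only and can resemble a treatment-period interaction, on whose absence the planned Wilcoxon analysis depends. The direction is clear; the size is unknown and may be small.

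The Group B-only argument assumes that the rocuronium ratings are taken at the intended depth. Those ratings carry a similar pair of rules: TOF=0 in Groups and three minutes in Surgical conditions. The sample size of 34 is unaffected.

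**What to change.** The sponsor should reconcile Groups, Medicine according to intervention and Surgical conditions so that:

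- every TOF/PTC state maps to exactly one reversal instruction;
- each mention of TOF is labelled as count or ratio;
- one trigger governs the Group B second rating, stated identically wherever it appears.

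The clinicians decide the content; no dose or threshold is suggested here. The same pass should check that the rocuronium ratings have a single timing rule.

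For the analysis, mark the time of each primary rating against the TOF/PTC values already recorded. Add a supportive sensitivity analysis of the primary outcome restricted to ratings taken at the reconciled criterion.

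The cost is a wording change to the protocol, one time mark per rating and one small extra analysis.

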Responsible for patient information and declaration of consent is local investigator. The patient will receive oral and written information about the project.

The initial contact with the patient will be done at a preoperative surgical evaluation at Herlev Hospital. The surgeon conducting the evaluation will handout the written patient information to all patients planned to have laparoscopic ventral-hernia surgery at Gentofte Hospital. The patient will at the same time receive a short oral information about the study and will be informed that the local investigator will contact the patient by telephone within a few days. This gives the patient time to read the information and to discuss it with family or relatives. The patient will be offered the possibility of being accompanied by a family member or another person at the telephone information interview. The local investigator will answer any question regarding the study and check that the inclusion criteria are met and none of the exclusion criteria are found. The patient will be offered a face-to-face interview if he/she wish. The patient will be informed that he/she will receive usual treatment if he/she does not want to participate, and that participation is voluntary, and that he/she always has the right to disclaim consent without affecting the further treatment.

After a period of consideration, depending on the patient's needs, an attempt will be made to obtain consent.

Pre-operative assessment:

In the Case Report Form (CRF) the following baseline data is noted:

Age

Weight

Height

Sex

BMI

Protocol
The hernia study
September 16. 2016

ASA group (I-IV)

Previous abdominal surgery

Co-morbidity which requires daily medical treatment

Parity

Randomization:

Randomization is 1:1, and done using Randomization.com. Two persons unattached to the study will use the randomization generator and pack the 34 envelopes consecutive numbered from 1 to 34. A paper revealing the intervention group assigned will be placed in each envelope. A copy of the randomization list will be kept in a sealed envelope by the coordinating investigator until the study is completed.

The randomization envelopes will be used in numerical order.

After randomization the investigator writes the randomization-group on the neuromuscular blockade sheet (NMB sheet).

34 eligible patients will be randomized.

Blinding:

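### The Mann-Whitney U test is described as comparing medians; for the event counts and the suturing rating it compares distributions, so a significant p value can sit beside equal medians with no effect measure to explain it

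*Combined protocol and SAP*

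**What the plan says.** The Statistics section of the combined protocol and SAP sets one rule for all variables that are not normally distributed: they are "expressed by medians and interquartile range and the Mann-Whitney U test used for comparison of the median values". It adds Fisher's exact test for percentages and the threshold "A p value < 0.05 is considered significant". It names no effect measure or confidence interval for between-group comparisons.

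The Outcomes section introduces the list to which the rule applies with "Secondary outcomes: (comparing Group A with Group B". Four of its seven items are discrete and ordered or counted:

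- One ordinal score, given as "Surgeon's rating of surgical conditions while suturing the hernia (5-point rating scale".
- A first event count, given as "Number of sudden contractions of the abdominal wall during operation (bucking or coughing".
- A second event count, taken from the insufflator and given as "Number of insufflator alarms where pneumoperitoneum > 17 mmHg".
- A third event count, for the tight-abdomen episodes, which begins "Number of episodes with continuous abdominal contractions".

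No expected event rate, share of zeros or rating distribution is given for any of them. The primary outcome has its own test, a Wilcoxon signed-rank test on within-patient differences, and does not fall under this rule.

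**The concern.** The Mann-Whitney reference distribution is derived under identical distributions in the two groups, and the statistic estimates P(A<B) + ½P(A=B). That amounts to a comparison of medians only if one distribution is a shifted copy of the other. A count with a floor at zero and a rating with five categories can hardly meet that condition.

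If fewer than half the patients in each group have an event, both medians are 0 whatever the treatment does, yet the test can still be significant. Read literally, the plan would then report a difference in medians that does not exist. It would also give no usable size for a real difference in events.

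**Working it through.** **Inputs.** Total 34 (Randomization; Sample size calculation). "Randomization is 1:1", so 17 v 17 if balanced (assumed). Level 0.05 (Statistics), taken as two-sided because the plan does not say.

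**The plan's own figure.** The 34 reproduces as a paired comparison with the SD of 2 read as the SD of differences. The normal approximation is (1.96 + 0.84)² × 2²/1² ≈ 31.4; with the t distribution it is 33.37, rounded up to 34. It does not bear on this point, for which the plan gives no figure.

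**Two possible data sets.** Let U = (pairs in which the Group B patient has fewer events) + ½(tied pairs). Under identical distributions:

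- mean = n₁n₂/2 = 17 × 17/2 = 144.5
- variance = (n₁n₂/12) × [(N+1) − Σ(t³−t)/(N(N−1))], with t the tie sizes, n₁n₂/12 = 24.083 and N(N−1) = 34 × 33 = 1122

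*Data set 1.* Group A: 17 zeros. Group B: eleven 0s, three 1s, two 2s, one 3.

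- U = 17 × 11/2 = 93.5, which is 51 below 144.5
- Σ(t³−t) = 21924 + 24 + 6 = 21954
- variance = 24.083 × (35 − 19.567) = 371.7, SD 19.28
- z with continuity correction = 50.5/19.28 = 2.62, p = 0.009
- median (IQR): 0 (0-0) v 0 (0-1)
- mean events: 0 v 10/17 = 0.59
- P(A better) + ½P(tie) = (17 × 6 + 93.5)/289 = 0.68

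*Data set 2.* Group A: 17 zeros. Group B: thirteen 0s and 1, 1, 2, 3.

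- U = 17 × 13/2 = 110.5, which is 34 below 144.5
- Σ(t³−t) = 26970 + 6 = 26976
- variance = 24.083 × (35 − 24.043) = 263.9, SD 16.24
- z = 33.5/16.24 = 2.06, p = 0.039
- median (IQR): 0 (0-0) v 0 (0-0)
- P(A better) + ½P(tie) = (17 × 4 + 110.5)/289 = 0.62

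These p values are asymptotic. In both sets all the events lie in one group, the most extreme split, so the exact two-sided permutation p is 2 × C(34−k, 17)/C(34, 17) for k patients with events. That gives 0.018 for k = 6 and 0.103 for k = 4. Data set 1 is significant either way. Data set 2 is significant only with the large-sample version, and the plan does not say which version is meant.

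**How often with equal medians.** Simulated rejection rates at 0.05, 17 v 17, both true medians equal. All distributions are assumptions.

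| Scenario | Rejects |
|---|---|
| Identical count distributions | 3% to 5% |
| Share with no event 0.95 v 0.90 | 4% |
| 0.95 v 0.80 | 24% |
| 0.95 v 0.70 | 52% |
| 0.95 v 0.51 | 91% |
| 1.00 v 0.51 | 99% |
| Poisson means 0.1 v 0.3 | 23% |
| Poisson means 0.1 v 0.69 | 80% |
| 5-point ratings, equal medians | 24% to 99% |
| Continuous times, unequal spread | 5% to 8% |

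**Does the planned IQR show the difference?** Among significant trials, median and both quartiles were identical in about 15% (any event in 5% v 30% of patients), 5% (5% v 40%) and 3% (2% v 45%). The medians alone were identical in about 92%, 74% and 64%.

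**The case against.** The strongest reply is that this is a common shorthand on secondary outcomes and that correcting it changes no p value. Several parts of that case stand.

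- **The rejection rates are not error rates.** A reader of the table might infer that the test is falsely positive in half or more of trials. It is not. Apart from the identical-distribution row, the simulated groups truly differ and the table shows power. Under identical distributions the rate is about 4.5%.
- **The rating scenarios are not artefacts of spread.** Two of those examined, both with true medians of 4, reject in about 55% and 96% of trials. Group A is better at every cut-point, with means of 4.15 v 3.50 and 4.40 v 3.38. The test correctly finds a real shift that the median misses.
- **The plan requires the IQR as well as the median.** One might infer that the planned table would hide the effect. Usually it would not: in data set 1 the upper quartile moves to 1, and complete agreement of median and quartiles is uncommon among significant trials.
- **Zero-heavy counts are assumed.** Group B is sutured without block, and the protocol provides for poor surgical conditions. If most Group B patients have events, equal medians of 0 no longer arise.
- **Fisher's exact test is already named for percentages.** On data set 1 it gives 0/17 v 6/17, p=0.018. But the plan does not commit to analysing the counts as any event v none.

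None of this makes the stated purpose of the test correct, and none supplies an effect measure.

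**Conclusion.** The point holds as a wrongly stated hypothesis and a weak effect summary for four of the seven secondary outcomes, to the extent that they are handled as non-normal. A significant result with equal medians is possible at this sample size, and the plan's wording would present it as a difference in medians. How often that would happen cannot be settled from the documents: with equal medians, rejection runs from about 4% to 99% depending on the assumed distributions.

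The documents do not support any reading in which the test is invalid, the type I error is inflated, the sample size is wrong or the primary conclusion is at risk. The conclusion rests on a 17 v 17 split, a two-sided 0.05 level and, for the 0 v 0 examples, most patients having no events. Data set 2 also depends on the asymptotic p value.

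**What to change.** In the Statistics section, replace the closing words of the Mann-Whitney sentence, which give comparison of medians as the test's purpose, with: *used to compare the distributions between groups*. State whether the p value is exact or asymptotic. Then specify what is reported:

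- **All Mann-Whitney comparisons:** the probability that a Group A patient does better than a Group B patient, ties counted half, with a 95% CI by a named method that allows for ties.
- **The three event counts:** also the number and proportion of patients with at least one event and the mean events per patient, by group. The CI for the difference in proportions must remain valid when one group has no events. A bootstrap does not, because a group of all zeros has no resampling variance. A Newcombe interval built from Wilson limits is one suitable choice.
- **The suturing rating:** the distribution over the five categories by group.
- **Conclusions:** worded in terms of these measures, not medians.

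The cost is SAP wording and a few lines of code on data already planned, with no extra patients or procedures. The downside is a less familiar effect measure and wide intervals at 17 per group.
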